10.2.2 Collection and Reporting of SAEs

When an SAE occurs through the AE collection period it should be reported according to the following procedure:

A Takeda SAE form must be completed, in English, and signed by the investigator immediately or within 24 hours of first onset or notification of the event. The information should be completed as fully as possible but contain, at a minimum:

- A short description of the event and the reason why the event is categorized as serious.
- Subject identification number.
- Investigator's name.
- Name of the study medication(s).
- Causality assessment.

The SAE form should be transmitted within 24 hours to the attention of the contact listed in Section 1.1.

Any SAE spontaneously reported to the investigator following the AE collection period should be reported to the sponsor if considered related to study participation.

Also, investigators should report any SAE in appropriate format (ie, locally required form) to related authorities, IRB/IECs in accordance with local GCP and/or local regulations.

Reporting of Serious PTEs will follow the procedure described for SAEs.

10.2.3 Reporting of Abnormal Liver Function Tests

If a subject is noted to have ALT or AST elevated $>3 \times \text{ULN}$ on 2 consecutive occasions, the abnormality should be recorded as an AE. In addition, an LFT Increases eCRF must be completed providing additional information on relevant recent history, risk factors, clinical signs and symptoms and results of any additional diagnostic tests performed.

If during the treatment or follow up period a subject is noted to have ALT or AST $>3 \times \text{ULN}$ and total bilirubin $>2 \times \text{ULN}$ for which an alternative etiology has not been identified, the event should be recorded as an SAE and reported as per Section 10.2.2. The investigator must contact the Medical Monitor for discussion of the relevant subject details and possible alternative etiologies, such as acute viral hepatitis A or B or other acute liver disease. Follow-up laboratory tests as described in Section 9.1.10 must also be performed. In addition, an LFT Increases eCRF must be completed and transmitted with the Takeda SAE form (as per Section 10.2.2).

10.3 Follow-up of SAEs

If information not available at the time of the first report becomes available at a later date, the investigator should complete a follow-up SAE form or provide other written documentation and fax it immediately within 24 hours of receipt. Copies of any relevant data from the hospital notes (eg, ECGs, laboratory tests, discharge summary, postmortem results) should be sent to the addressee, if requested.

All SAEs should be followed up until resolution or permanent outcome of the event. The timelines and procedure for follow-up reports are the same as those for the initial report.

10.3.1 Safety Reporting to Investigators, IRBs or IECs, and Regulatory Authorities

The sponsor will be responsible for reporting all suspected unexpected serious adverse reactions (SUSARs) and any other applicable SAEs to regulatory authorities, investigators and IRBs or IECs, as applicable, in accordance with national regulations in the countries where the study is conducted. Relative to the first awareness of the event by/or further provision to the sponsor or sponsor's designee, SUSARs will be submitted within 7 days for fatal and life-threatening events and 15 days for other serious events, unless otherwise required by national regulations. The sponsor will also prepare an expedited report for other safety issues where these might materially alter the current benefit-risk assessment of an investigational medicinal product or that would be sufficient to consider changes in the investigational medicinal products administration or in the overall conduct of the trial. The investigational site also will forward a copy of all expedited reports to his or her IRB or IEC in accordance with national regulations.

11.0 STUDY-SPECIFIC COMMITTEES

No steering committee, data safety monitoring committee, or clinical endpoint committee will be used in this study.

12.0 DATA HANDLING AND RECORDKEEPING

The full details of procedures for data handling will be documented in the Data Management Plan. AEs, PTEs, medical history, and concurrent conditions will be coded using the Medical Dictionary for Regulatory Activities (MedDRA). Drugs will be coded using the World Health Organization Drug Dictionary (WHODRUG).

12.1 eCRF

Completed eCRFs are required for each subject who signs an informed consent.

The sponsor or its designee will supply investigative sites with access to eCRFs. The sponsor will make arrangements to train appropriate site staff in the use of the eCRF. These forms are used to transmit the information collected in the performance of this study to the sponsor and regulatory authorities. eCRFs must be completed in English. Data are entered directly onto eCRFs.

After completion of the entry process, computer logic checks will be run to identify items, such as inconsistent dates, missing data, and questionable values. Queries may be issued by Takeda personnel (or designees) and will be answered by the site.

Corrections are recorded in an audit trail that captures the old information, the new information, identification of the person making the correction, the date of the correction was made and the reason for change. Reasons for significant corrections should additionally be included.

The principal investigator must review the eCRFs for completeness and accuracy and must sign and date the appropriate eCRFs as indicated. Furthermore, the investigator must retain full responsibility for the accuracy and authenticity of all data entered on the eCRFs.

eCRFs will be reviewed for completeness and acceptability at the study site during periodic visits by study monitors. The sponsor or its designee will be permitted to review the subject's medical and hospital records pertinent to the study to ensure accuracy of the eCRFs. The completed eCRFs are the sole property of the sponsor and should not be made available in any form to third parties, except for authorized representatives of appropriate governmental health or regulatory authorities, without written permission of the sponsor.

12.2 Record Retention

The investigator agrees to keep the records stipulated in Section 12.1 and those documents that include (but are not limited to) the study-specific documents, the identification log of all participating subjects, medical records, temporary media such as thermal sensitive paper should be copied and certified, source worksheets, all original signed and dated informed consent forms, subject authorization forms regarding the use of personal health information (if separate from the informed consent forms), electronic copy of eCRFs, including the audit trail, and detailed records of drug disposition to enable evaluations or audits from regulatory authorities, the sponsor or its designees. Furthermore, International Conference on Harmonisation (ICH) E6 Section 4.9.5 requires the investigator to retain essential documents specified in ICH E6 (Section 8) until at least 2 years after the last approval of a marketing application for a specified drug indication being investigated or, if an application is not approved, until at least 2 years after the investigation is

discontinued and regulatory authorities are notified. In addition, ICH E6 Section 4.9.5 states that the study records should be retained until an amount of time specified by applicable regulatory requirements or for a time specified in the Clinical Study Site Agreement between the investigator and sponsor.

Refer to the Clinical Study Site Agreement for the sponsor's requirements on record retention. The investigator should contact and receive written approval from the sponsor before disposing of any such documents.

13.0 STATISTICAL METHODS

13.1 Statistical and Analytical Plans

A statistical analysis plan (SAP) will be prepared and finalized prior to unblinding of subject's treatment assignment. This document will provide further details regarding the definition of analysis variables and analysis methodology to address all study objectives.

A blinded data review will be conducted prior to unblinding of subject's treatment assignment. This review will assess the accuracy and completeness of the study database, subject evaluability, and appropriateness of the planned statistical methods.

13.1.1 Analysis Sets

The full analysis set (FAS) will be defined separately for the Healing and Maintenance Periods. The full analysis set for the Healing Period (FAS – H) will include all randomized subjects who have documented EE at screening and receive at least 1 dose of study drug during the first 8 weeks of treatment. The full analysis set for the Maintenance Period (FAS – M) will include all subjects with healed EE by week 8 who are randomized and receive at least 1 dose of study drug during 6 months of maintenance treatment.

The safety analysis set will be defined separately for the healing period and for the Maintenance Period. The safety analysis set for the Healing Period (Safety Set – H) will include all subjects who receive at least 1 dose of study drug during Healing Period. The safety analysis set for the Maintenance Period (Safety Set – M) will include all subjects with healed EE by Week 8 who are randomized and receive at least 1 dose of study drug during 6 months of maintenance treatment.

13.1.2 Analysis of Demographics and Other Baseline Characteristics

Demographic and baseline variables will be summarized using the safety analysis set and analyzed to assess the comparability of the treatment groups provided by randomization. Summary statistics (N, mean, median, SD, and range) will be generated for continuous variables (eg, age and weight). The numbers and percentages of subjects will be presented for categorical variables (eg, gender, race).

13.1.3 Efficacy Analysis

The primary efficacy variable will be the percentage of subjects who have complete healing of EE over 8 weeks as assessed by endoscopy. The treatment difference of healing rate between dexlansoprazole and lansoprazole will be calculated and the lower bound of 95% confidence interval will be compared with -10%. Noninferiority to lansoprazole will be declared if the lower bound is greater than -10%. Subjects who do not have endoscopically documented healing and who prematurely discontinue will be considered as not healed.

The secondary efficacy variable will be the percentage of subjects who maintained complete healing of EE over 6 months as assessed by endoscopy. A comparison between dexlansoprazole capsules and placebo will be made using Cochran-Mantel-Haenszel (CMH) test using

stratification factor of baseline grade. Subjects who do not have endoscopically documented maintenance of healing and who prematurely discontinue will be considered to have relapsed.

An additional efficacy variable will be the severity of GERD symptoms at Weeks 4 and 8 as assessed by the investigator during the Healing Period. The severity of GERD will be compared between dexlansoprazole and lansoprazole capsules using a CMH test for ordered responses with baseline severity as the stratum. The number of subjects at each severity level for each GERD symptom at Months 1, 3, 6 will be also summarized by treatment group and baseline severity. At each visit, the severity will be compared between treatment groups using a CMH test for ordered responses (row mean score statistic with table scores of 0, 1, 2, 3, and 4) with baseline severity as the strata.

The percentage of days with neither daytime nor nighttime heartburn and the percentage of days without rescue medication use over the 8 weeks of the Healing Period and over the 6 months of the Maintenance Period as assessed by the daily diary will be summarized by treatment groups. Comparisons between treatment groups will be made using Wilcoxon rank-sum tests.

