6.0 STUDY DESIGN AND DESCRIPTION

6.1 Study Design

This is a phase 3, randomized, double-blind, multicenter, active-controlled, 2-arm study with an initial 8-week healing period with noninferiority design, followed by a randomized, placebo-controlled 6-month maintenance period. The study is designed to evaluate healing, maintenance of healed EE and the effect of therapy on relieving GERD-related symptoms. Approximately 450 subjects will be enrolled at an estimated 25 sites across China.

The study consists of 3 periods; a Screening Period (maximum 21 days), a Healing Period, which will last 8 weeks, and a Maintenance Period of up to 6 months. After signing an informed consent form (ICF) subjects will undergo a screening evaluation within 21 days prior to the first dose of study drug (Study Day 1). Subjects will be instructed that lifestyle or behavior modifications designed to treat their symptoms of GERD should not be altered throughout the study. Subjects will be given a diary on the first day of the Screening Period. Throughout the Screening Period, subjects will record the presence and maximum severity of daytime and nighttime heartburn symptoms each day in their diary.

During the Screening Period, subjects will undergo various procedures to determine eligibility for the Healing Period. Screening evaluations will include the following: demographics, medical and social history, physical examination including vital signs, height and weight, ECG, endoscopy, clinical laboratory evaluations including tests for serum and urine pregnancy (all women of childbearing potential) and hepatitis panel, and concomitant medication assessment. The screening clinical laboratory tests, hepatitis panel, and endoscopy must be performed within 14 days prior to randomization. Endoscopy data will be collected to identify subjects with EE, and only those subjects with endoscopically-confirmed EE Grades A-D as defined by the LA Classification Grading System ([Appendix E](#)), will be eligible for this study. Endoscopic pictures will be taken by the study site and kept in the site's source document files according to the site's practice.

Subjects who satisfy the screening evaluation and selection criteria, and have EE confirmed by endoscopy, may be entered into the study. Subjects having an esophageal stricture will be excluded from the study. The endoscope must pass freely into the stomach during the endoscopy.

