All subjects will return to the investigative site on Day -1 which will be deemed as the Baseline. Subjects who have completed all of the Screening procedures and met all eligibility requirements and none of the exclusion criteria will have routine fasting laboratory evaluations, including fasting serum gastrin, a urine pregnancy test (all women of childbearing potential), physical examination, and vital signs measurements to assure continued eligibility. Subjects will be dispensed study drug on Study Day -1 according to an interactive web response system (IWRS) and will begin taking study drug on the following day (Study Day 1). In addition, subjects will be assessed for GERD symptoms such as heartburn, acid regurgitation, dysphagia, belching, and epigastric pain by the investigator.

- Subjects will be assigned in a 1:1 ratio to one of the following 2 treatment groups during the 8-week Healing Period; the randomization will be stratified by baseline endoscopic findings (grades A/B or C/D).
 - Group I: dexlansoprazole capsules (60 mg QD)
 - Group II: lansoprazole capsules (30 mg QD)

During the 8-week Healing Period, study drug will be self-administered orally QD before breakfast in the morning. Subjects will document the presence and maximum severity of daytime and nighttime heartburn symptoms using a diary. Subjects will also record the use of rescue medication. Subject visits will be conducted at Weeks 4 and 8 of the Healing Period to collect and/or dispense study drug, assess GERD symptoms, review concomitant medication use, and assess AEs.

At the Week 4 Visit, the subject will undergo a physical examination including vital signs, laboratory evaluations, and urine pregnancy test (all women of childbearing potential).

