7.4 Diet, Fluid, Activity Control

The principal investigator, the coinvestigators, and the study collaborators are to explain, and give instructions on, the following before the start of the study or during the study, as well as to check to see if the subjects keep to the instructions at the time of their scheduled visits.

- Every subject should keep to the scheduled visits, seek medical consultation, and undergo predetermined laboratory.
- The subject should ensure that all study medications are swallowed with approximately 240 mL water according to the administration, and dosing schedule. Subjects should be instructed according to Section 8.1.3.1 (Missed Doses) and 9.2 (Compliance). Details of any missed or forgotten doses should be reported to the Investigator or designee at the subsequent study visit.
- The subject should store all medications in a cool, dry, safe place which is out of reach of children and to bring all study supplies (empty / used / unused drug packets and diaries alike) to each study visit.

- The subject should record his/her nighttime (during sleep) subjective symptoms and the previous daytime subjective symptoms in his/her subject diary upon rising in the morning on a daily basis. The subject should also record the use of rescue medication since the start of the Screening Period as well as his/her study medication compliance status during the Treatment Phase.
- The subject will be required to fast for at least 8 hours before each visit at which fasted blood tests will be drawn and/or endoscopy will be performed, after the ICF is signed. Fasting is defined as no food or nutritional drinks for 8 hours before the blood draw. Water is allowed. Any medication that needs to be taken with food and any study medications should be held until after the fasting blood has been drawn and/or the endoscopy has been performed. Medication that does not need to be taken with food should be continued. The investigator must instruct the subject accordingly prior to visits in which serum gastrin is measured and endoscopy is performed.
- After the first dose of study drug during the Healing Period and the Maintenance Period, the subject should present to the clinic in the morning as scheduled.

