9.1.7 Daily Diary

Subjects will be given paper diaries on the first day of the Screening Period. Throughout the Screening Period, Healing Period, and Maintenance Period, subjects will document the presence and maximum severity of daytime and nighttime heartburn symptoms each day in their daily diary. Subjects will also record the use of rescue medication. If the subject experiences no heartburn on any given day, they should also provide this information. The daily diary should be completed every morning upon waking and every evening before bedtime. The last entry for the Healing Period is in the morning prior to their Week 8/Final Visit site visit. The last entry for the Maintenance Period is in the morning prior to the subject's Month 6/Final Visit site visit.

The paper diaries will be collected and reviewed at subsequent visits. Subjects must return their daily dairies at every visit. The severity of heartburn will be graded by the subject according to the definitions outlined in [Appendix G](#). Should paper diaries be lost or destroyed, the subject should contact the site immediately to receive additional diary pages to insure continuity of symptom reporting.

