9.3.1 Screening

Subjects will be screened within 21 days prior to randomization. Subjects will be screened in accordance with predefined inclusion and exclusion criteria as described in Section 7.0. See Section 9.1.14 for procedures for documenting screening failures.

The screening clinical laboratory tests, hepatitis panel, and endoscopy must be performed within 14 days prior to randomization.

Any reliable, documented results available from an endoscopy performed in a routine clinical setting (before signing of informed consent) in the same institution will be accepted instead, given the invasive nature of the procedure.

Screening laboratory results from the TAK-390MR_302 study performed in the same institution can be accepted as a screening laboratory results in TAK-390MR_301 study, on a case-by-case basis, given the burden of frequent blood draws in a short period of time. The investigator must contact the medical monitor for a discussion of the relevant subject details before subject's randomization.

Procedures to be Completed During the Screening Period (Days -21 to -2) include:

- Informed consent.
- Demographics, medical, and social history.
- Medication history.
- Physical examination.
- Vital signs.
- Weight and height.
- Concomitant medication(s).
- Concurrent medical condition(s).
- Pretreatment events assessment.
- Prescribe rescue medication and give the medical instruction, as necessary.
- Screening clinical laboratory tests and hematology (to be performed within 14 days prior to randomization).
- Urinalysis.
- Serum and urine hCG (women of childbearing potential only).
- FSH (only performed if menopause is suspected).
- Guidance on the avoidance of pregnancy.
- Instructions on how to make entries in the subject diary, provision of the diary, and commencement of diary entry.

- ECG.
- Hepatitis panel including HBsAg and HCV-antibody (to be performed within 14 days prior to randomization).
- Endoscopy (to be performed within 14 days prior to randomization).

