7.8.3 Additional Efficacy Endpoints

All additional efficacy variables will only be presented in data listings, no summary tables will be produced. The following are the additional efficacy variables to be listed:

The severity of GERD symptoms at Weeks 4 and 8 as assessed by the investigator during the Healing Period.

The percentage of days with neither daytime nor nighttime heartburn and the percentage of days without rescue medication use over the 8 weeks of the Healing Period and over the 6 months of the Maintenance Period as assessed by the daily diary.

- The severity of daytime and nighttime heartburn over the 8 weeks of the Healing Period and over the 6 months of the Maintenance Period as assessed by daily Diary.
- The severity of nighttime heartburn over the 8 weeks of the Healing Period and over the 6 months of the Maintenance Period as assessed by daily Diary.
- The severity of daytime heartburn over the 8 weeks of the Healing Period and over the 6 months of the Maintenance Period as assessed by daily Diary.

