Appendix D Data Handling for Subject Daily Diary

Subjects will document the presence of daytime and nighttime heartburn(yes/no) and maximum severity (1=Mild, 2=Moderate, 3=Severe, or 4=Very Severe) and record their usage of rescue medication (yes/no) in their diary two times per day, once in the morning for nighttime heartburn and once in the evening for daytime heartburn. If a subject indicated that no heartburn was present during a diary entry, a heartburn severity of '0=None' will be assumed in the database.

For analysis purposes, diary entries will be assigned to a study day based on the day the collection interval started for that entry. For example, the Study Day 1 diary entries will include the evening diary completed on Study Day 1 (the collection interval started when the subject awoke on Study Day 1) and the morning entry completed on Study Day 2 (the collection interval started when the subject went to bed on Study Day 1).

For each subject, the percentage of days with neither daytime nor nighttime heartburn during treatment will be calculated using all days with at least 1 morning or evening diary entry during the Healing Period and during the Maintenance Period. For example, if a subject completed at least 1 diary entry on 52 of 56 days during the Healing Period, but missed both entries on 4 days, 52 days will be used as the denominator in the analysis. All entries on that day will need to be heartburn-free (when only one entry collected, that entry will need to be heartburn-free) in order for the day to be counted as a day with neither daytime nor nighttime heartburn.

A similar approach will be used to determine the percentage of days without rescue medication during treatment (the denominator would be total number of days with either a daytime or night time result marked during the Healing or Maintenance period).

The mean severity of daytime and nighttime heartburn during the Healing and Maintenance Periods for each subject will be calculated by taking the mean of the average severity on all days with at least one morning or evening diary entry. For each day, the average severity for the day will be determined by taking the mean of the morning and evening diary entries on that day. If one entry is missing, the average for the day will be the non-missing diary entry. These daily averages will then be averaged for all days with non-missing data to obtain the endpoint value for each subject.

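### The Protocol compares the diary endpoints with an unadjusted rank-sum test and the SAP only lists them, although a screening diary and the LA-grade strata would allow a more precise analysis

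*Protocol*

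**What the plan says.** **Planned test.** Protocol 13.1.3 summarises the two diary percentages by treatment group, in the Healing and the Maintenance Period, and then states: "Comparisons between treatment groups will be made using Wilcoxon rank-sum tests". Neither a baseline value nor a stratum enters. In the same section, the secondary endpoint has a CMH test stratified by baseline grade, and investigator-rated GERD severity has a CMH test stratified by baseline severity.

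**Data available before treatment.** Protocol 6.1: "Throughout the Screening Period, subjects will record the presence and maximum severity of daytime and nighttime heartburn symptoms each day in their diary". For rescue use, Protocol 7.4: "The subject should also record the use of rescue medication since the start of the Screening Period". Appendix H asks about heartburn and rescue use every morning and every evening. Both randomizations are stratified by LA grade A/B versus C/D (Protocol 6.1 and 8.3).

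**SAP.** Section 7.8.3 plans no comparison: "All additional efficacy variables will only be presented in data listings, no summary tables will be produced". Section 7.13 records no changes. In Appendix D the percentage of heartburn-free days "will be calculated using all days with at least 1 morning or evening diary entry during the Healing Period and during the Maintenance Period"; no screening-period value is derived.

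**The concern.** The same questions are asked on the same instrument before and after randomization. A subject's screening percentage is therefore a natural covariate for the on-treatment percentage, and the LA strata were built into the design. The rank-sum test uses neither. The Protocol adjusts its other symptom comparison for baseline severity and gives no reason for treating the diary differently.

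These are the only subject-reported efficacy comparisons that the Protocol plans; the GERD severity scores are the investigator's. If subjects differ widely in symptom frequency before treatment, leaving that out widens the uncertainty about the treatment difference and leaves any chance imbalance between the arms uncorrected. No sample size was set for these endpoints, so data already collected are the one available source of extra precision.

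**Working it through.** **1. The plan's own figure.** The documents give no power, SD or effect size for any diary endpoint. The diary comparison inherits its numbers from the primary endpoint (Protocol 13.2: 85% healing in both arms, margin 10 points, 1-sided 0.025, 80% power, 10% dropout):

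- n per arm = (1.960 + 0.842)² × 2 × 0.85 × 0.15 / 0.10² = 200.2, rounded up to 201.
- With dropout: 201 / 0.90 = 223.3, rounded up to 224, against 225 stated.

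The figure reproduces, but it says nothing about the diary. It only fixes 225 per arm as the size to work with.

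**2. Gain from the screening diary.** Let r be the correlation between screening and on-treatment values. Adjustment multiplies the variance by 1 − r², which is worth a factor of 1/(1 − r²) in sample size. As a reference, take a comparison with 80% unadjusted power at 225 per arm, 2-sided 0.05. That is a difference of (1.960 + 0.842) × √(2/225) = 0.264 SD. Adjusted power is Φ(2.802/√(1 − r²) − 1.960). The value of r is assumed.

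| r | Variance removed (r²) | Sample-size factor | Power, from 80% |
|---|---|---|---|
| 0.1 | 1% | 1.01 | 80.4% |
| 0.3 | 9% | 1.10 | 83.6% |
| 0.5 | 25% | 1.33 | 89.9% |
| 0.6 | 36% | 1.56 | 93.8% |

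**3. Check by simulation.** The outcome was a bounded percentage in steps of 1/56, the baseline was in steps of 1/14, and there were 225 subjects per arm and 4,000 runs. The effect was 1.02 × 0.264 SD on the underlying scale.

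| r | Rank-sum power | Rank ANCOVA power |
|---|---|---|
| 0 | 78.4% | 78.4% |
| 0.3 | 78.7% | 82.7% |
| 0.5 | 79.5% | 89.3% |

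With no treatment effect (1,500 runs per setting, r from 0 to 0.7), both tests rejected in about 4% to 6% of runs. Adjustment cost nothing when the baseline was uninformative. The simulation did not model the noise of a very short screening diary, nor the strata.

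**4. Gain from LA grade alone.** Protocol 4.1 puts grades C and D at about 25% of patients; this is background, not a planned stratum size. For an assumed standardized gap d between strata, v = 0.25 × 0.75 × d² and R² = v/(1 + v):

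- d = 0.2: 0.0075/1.0075 = 0.7%; power 80.3%.
- d = 0.5: 0.0469/1.0469 = 4.5%; power 81.8%.
- d = 0.8: 0.12/1.12 = 10.7%; power 84.3%.

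**5. What the documents imply about r.**

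- Screening runs from Day -21 to Day -2 (Protocol 9.3.1), with no minimum number of diary days.
- A routine endoscopy done before consent may be accepted (9.1.16), so some subjects may have few screening days. That makes their baseline noisy and lowers r.
- Entry requires endoscopic EE but no minimum heartburn (7.1). The resulting mix of subjects could push r either way.

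**6. Maintenance Period.** Subjects are re-randomized after 8 weeks of active treatment, and SAP 7.1.1 sets the Maintenance baseline at Week 8. The screening percentage is a legitimate pre-randomization covariate there, but not the obvious one. The documents define no diary baseline for this period.

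**The case against.** The strongest reply is that the SAP runs no test on these endpoints, so there is no comparison whose precision could be lost. This stands, and it sets the order of work: the conflict between Protocol 13.1.3 and SAP 7.8.3 comes first. If the sponsor deliberately drops the comparison, the Protocol text should change and this point lapses.

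Three further replies also stand:

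- The rank-sum test remains valid under stratified randomization. A reader might infer an inflated error rate or a biased comparison; neither follows.
- The endpoints are additional and unpowered, and no conclusion on healing or maintenance of healing depends on them.
- The baseline is not ready-made. SAP Appendix D derives nothing for screening, and the number of screening days varies.

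A reader might also take the gain to be large, say 10% to 56% more subjects for free. Those figures belong to r = 0.3 and r = 0.6. The documents give no r, and at 0.1 the gain is about 1%.

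It can be added that Protocol 13.1.3 already plans a baseline-stratified comparison of investigator-rated symptoms, heartburn among them. That softens the point under the Protocol. It does not under the SAP, which reduces all additional efficacy variables to listings.

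**Conclusion.** The point holds as a modest, optional improvement. The Protocol's test ignores a baseline that is collected and strata that were used to randomize; the SAP drops the test altogether without recording a change. The loss is one of efficiency and of protection against chance imbalance, not of validity.

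For the Healing Period, the variance left on the table ranges from about 1% (r = 0.1) to 36% (r = 0.6). This rests wholly on an assumed r and on a screening diary long enough to be informative. LA grade alone is worth about 1% to 5% of the variance for standardized gaps of 0.2 to 0.5. These figures should not be carried over to the Maintenance Period, where the natural covariate is a different one.

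**What to change.** 1. **Reconcile Protocol 13.1.3 with SAP 7.8.3.** Either write the diary comparison into the SAP or remove it from the Protocol, and record the change.
2. **Healing Period, if the comparison is kept.** In SAP Appendix D, derive the screening-period percentages of heartburn-free and rescue-free days by the same day rule as on treatment. State a minimum number of diary days and a rule for missing baselines that keeps those subjects in the analysis. Replace the rank-sum test with rank analysis of covariance on that baseline, stratified by LA grade (A/B versus C/D).
3. **Maintenance Period.** Choose one analysis for the whole comparison: a van Elteren test stratified by LA grade, or rank analysis of covariance on a diary baseline taken before re-randomization, such as the last Healing Period diary days. The method should not switch subject by subject according to whether a baseline exists.
4. **Timing.** Fix all of this before unblinding, when Protocol 13.1 requires the SAP to be final.

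The cost is a screening-period derivation (plus a Maintenance baseline if that option is chosen), its missing-data rule, wording in both documents and a little programming. No new data are needed. In the simulation, nothing was lost when the baseline was uninformative.
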